8.2 SAMPLE SIZE DETERMINATION

The goal of this pilot study was to collect preliminary data regarding the feasibility and acceptability of a meal delivery intervention among postpartum women. As this is a feasibility pilot with the primary goal of capturing process data, a formal power calculation was not conducted. Indeed, effect estimates based on small pilot studies are too imprecise and should not be used to inform future trials.⁹⁶ Instead, we followed recommendations from the National Center for Complementary and Integrative Health (NCCIH) that sample sizes for feasibility studies should be based on “practical considerations including participant flow, budgetary constraints, and the number of participants needed to reasonably evaluate feasibility goals.” With these considerations in mind, the present study aimed to recruit a minimum of 10 participants and up to 20 participants based on the available budget. This was a single-group trial with the primary goal being to obtain process data and preliminary data to inform intervention refinements before pursuing funding for subsequent pilot testing.

8.3 STATISTICAL ANALYSES

8.3.1 GENERAL APPROACH

At each time of measurement, descriptive statistics will be used to summarize demographic characteristics and process measures, including rates of study participant, retention, and intervention adherence. Average values of outcome measures (e.g., diet satisfaction) will be calculated for baseline and follow-up. No formal statistical analyses will be conducted as this was a single group feasibility study that was not designed to be powered to detect statistical significance.

8.3.2 ANALYSIS OF THE PRIMARY EFFICACY ENDPOINT(S)

For the primary endpoint of participant intervention adherence, the proportion of weekly study meals that participants reported a)they consumed, b) other household members consumed, and c) that were thrown away/uneaten will be calculated based on completed weekly electronic surveys.

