5 STUDY INTERVENTION

5.1 STUDY INTERVENTION(S) ADMINISTRATION

5.1.1 STUDY INTERVENTION DESCRIPTION

After completing baseline data collection, all participants will receive 10 fully prepared lunch/dinner-style meals per week for a total of 8 weeks. Prior studies indicate that providing 10 meals or meal replacements per week is effective for weight management.^{43,86} We are partnering with a local company, Nourish Foods, to prepare and deliver study meals. Participants will select the 10 meals that they want each week from a weekly rotating menu that includes nutrition and ingredient information to accommodate participants with food aversions or allergies. Participants place meal orders weekly with study staff who will submit orders to the meal delivery partner. During these weekly contacts, trained staff also provide brief behavioral support, including evidence-based strategies of problem-solving, action-planning, and principles of motivational interviewing to help participants identify and navigate adherence barriers.⁸⁷⁻⁹¹ Staff will document the duration and topics discussed. Each week of the intervention, participants will be automatically sent an electronic survey to report the number of study-provided meals consumed by participants (versus others in the household versus thrown out), as we understand meals may be shared in food insecure households. The study coordinator will be available when collecting weekly meal orders to help participants navigate these challenges in multi-member households. If a participant does not place their weekly order, study staff will select meals based on participant preferences and allergies collected at baseline. Meals will be delivered once per week to participants' homes, which is in compliance with the Alabama Department of Public Health guidelines.

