5.1.2 DOSING AND ADMINISTRATION

Participants in the study receive 10 lunch/dinner-style meals per week delivered to their homes free of charge for a total of 8-weeks. Participants will select the 10 meals that they want each week from a weekly rotating menu that includes nutrition and ingredient information to accommodate participants with food aversions or allergies. Participants place meal orders weekly with study staff who will submit orders to the meal delivery partner. If a participant does not place their weekly order, study staff will select meals based on participant preferences and allergies collected at baseline to ensure they receive meals each week. Each week of the intervention, participants will be automatically sent an electronic survey to report the number of study-provided meals consumed by participants (versus others in the household versus thrown out).

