5.2 STUDY INTERVENTION COMPLIANCE

Participants place meal orders weekly with study staff who will submit orders to the meal delivery partner. If a participant does not place their weekly order, study staff will select meals based on participant preferences and allergies collected at baseline to ensure they receive meals each week. Each week of the intervention, participants will be automatically sent an electronic survey to report the number of study-provided meals consumed by participants (versus others in the household versus thrown out). Study staff completing weekly check-in calls with participants will document the duration and topics discussed.

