6.3 LOST TO FOLLOW-UP

A subject will be considered lost to follow-up if he or she fails to complete 3 scheduled check-in visits in a row or fails to complete the follow-up visit and is unable to be contacted by the study site staff.

The following actions must be taken if a subject fails to be available for a required study visit:

- The site will attempt to contact the subject and reschedule the missed visit and counsel the subject on the importance of maintaining the assigned visit schedule and ascertain if the subject wishes to and/or should continue in the study.
- Before a subject is deemed lost to follow-up, the investigator or designee will make every effort to regain contact with the subject (where possible, 3 telephone calls and, if necessary, a certified letter to the subject's last known mailing address or local equivalent methods). These contact attempts should be documented in the subject's medical record or study file.
- Should the subject continue to be unreachable, he or she will be considered to have withdrawn from the study with a primary reason of lost to follow-up.

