8 STATISTICAL CONSIDERATIONS

8.1 STATISTICAL HYPOTHESES

- Primary Efficacy Endpoint(s): The primary aim of this study is to assess the feasibility of the study meal delivery intervention. Hypothesis 1: We will successfully achieve >80% intervention adherence, defined as consuming at least 80% of received study meals, during the 8-week intervention.
- Secondary Efficacy Endpoint(s): The secondary aim is to characterize the acceptability of the study meal delivery intervention. Hypothesis 2a: We will collect data to characterize study participation rate and achieve <20% attrition. Hypothesis 2b: Participant reported diet satisfaction will show improvements from baseline to follow-up.

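### The primary >80% adherence target is set over received meals (8.1) but calculated from completed surveys (8.3.2), so weeks with meals and no survey drop out of the figure

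*Combined protocol and SAP*

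**What the plan says.** Hypothesis 1 in section 8.1 expects more than 80% intervention adherence, "defined as consuming at least 80% of received study meals, during the 8-week intervention". The base is received meals over the whole intervention.

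Section 8.3.2 gives the primary analysis. It takes the weekly meals that the woman ate, that others in the household ate, and those discarded; the proportions for all three, including those "thrown away/uneaten will be calculated based on completed weekly electronic surveys", rest on the surveys returned. It does not say how a week without a survey is treated.

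Supply and reporting are separate processes. On supply, section 5.1.1 says: "If a participant does not place their weekly order, study staff will select meals", and section 5.2 gives the purpose: "to ensure they receive meals each week". On reporting, section 5.1.2 says that each week "participants will be automatically sent an electronic survey to report the number of study-provided meals consumed by participants".

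The analysis is descriptive. Under section 8.3.1, "descriptive statistics will be used to summarize demographic characteristics and process measures", and there is no formal testing. Section 8.2 says the results are to guide refinement of the intervention before funding is sought for further pilot work.

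**The concern.** The two sections describe the same quantity only if every received meal is covered by a returned survey. A woman who disengages can go on receiving meals while reporting nothing. The completed-survey calculation leaves her silent weeks out, although the meals in them belong to the base defined in 8.1.

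If women eat fewer study meals in the weeks they do not report, the published figure overstates adherence. That is plausible, but the documents do not establish it. The gift cards in section 4.4 reward the baseline and follow-up visits, not the weekly surveys. The weekly calls record duration and topics (5.2, 7.1), and no meal count is mentioned. The query step for missing data in 9.1.4 may recover some reports, but it does not say how a week that stays unreported counts.

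At stake is the statement that the primary feasibility target was or was not met. No error rate is involved, and no stop/go decision is tied to the figure.

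A related gap concerns the unit. Section 8.1 uses 80% twice, once as a target and once inside the definition of adherence. It can be read as a pooled proportion of meals, a mean over participants, or the share of participants who ate at least 80% of their meals.

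**Working it through.** **Inputs from the documents.** 10 meals a week for 8 weeks (5.1.1) is 80 meals per woman. With N = 11 (1.1, 7.1) that is 880 meals and 88 weekly surveys. The target is >80% (8.1). The plan has no power calculation or other derived figure to reproduce.

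**Assumptions.** Survey completion c and reported adherence a are not in the documents. They are varied below, on a pooled reading.

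**Error of the completed-survey figure.** Adherence over received meals is ca + (1-c)m. The completed-survey figure is a. The difference is

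a - [ca + (1-c)m] = (1-c)(a-m).

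It is zero when c = 1 or m = a, positive (overstated) when m < a, and negative when m > a. For example, a = 0.85, c = 0.90 and m = 0.35 give 0.10 × 0.50 = 0.05, so a reported 85% is really 80%.

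**Bounds.** Setting m = 0 gives the lower bound ca, and m = 1 gives the upper bound ca + (1-c). The break-even value of m is (0.80 - ca)/(1-c). The bounds straddle 80% when a lies between (0.80 - (1-c))/c and 0.80/c.

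| Completion c | Bounds at a = 85% | Break-even m at a = 85% | Reported adherence for which bounds straddle 80% |
|---|---|---|---|
| 80% | 68% to 88% | 60% | 75% to 100% |
| 90% | 76.5% to 86.5% | 35% | 77.8% to 88.9% |
| 95% | 80.75% to 85.75% | none; lower bound is above 80% | 78.9% to 84.2% |

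At a = 85% the lower bound stays above 80% only if completion exceeds 0.80/0.85 = 94.1%. That allows at most 5 missing surveys of 88: 0.85 × 83/88 = 80.2%, and 0.85 × 82/88 = 79.2%.

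**Unit, with complete data.** Let ten women eat 8 of 10 meals each week and one eat 6 of 10. Pooled: (10 × 64 + 48)/880 = 688/880 = 78.2%, target missed. The participant mean is also 78.2%. Share of women at 80% or more: 10/11 = 90.9%, target met.

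**Unit, with missing surveys.** Let all 11 women eat 9 of 10 in reported weeks and each miss one survey. The completed-survey figure is 90%. Each woman's lower bound is 63/80 = 78.8% and her upper bound is 73/80 = 91.3%. On the share reading the bounds run from 0/11 to 11/11, so they must be computed on the chosen unit.

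**The case against.** The strongest reply is that 8.3.2 does contain a rule. Weekly meals calculated from completed surveys is a terse but usable available-week analysis. That is right, and a reader who inferred that the plan has no rule at all for unreported weeks would go too far. What stands is that this rule estimates something other than the received-meals quantity in 8.1, with no check on the difference.

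Second, the analysis is descriptive, retention and participant flow are reported (8.3.3), missing data are queried (9.1.4), and completion may turn out high. All of this stands and limits the stakes.

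Third, a reader might infer from the protocol's own limits that the verdict will flip. Hypothesis 2a says "We will collect data to characterize study participation rate and achieve <20% attrition", which allows 2 of 11 women (18.2%). Under 6.3 a woman who cannot be contacted is lost if she "fails to complete 3 scheduled check-in visits in a row". Suppose two women each leave 3 delivered weeks unreported (60 meals), the other nine report fully, and reported adherence is 85%. Counting the 60 meals as not eaten gives 612/780 = 78.5% if the two never report, or 697/880 = 79.2% if they report for 5 weeks first. The documents do not support this as more than an illustration:

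- Section 6.3 counts missed check-ins, not missed surveys, and the survey is sent separately.
- Section 2.3.1 has delivery times arranged with participants, so receipt by a woman out of contact is not assured.
- The 85% is assumed.
- On the share reading, with nine women at 85% and both lost women counted as non-adherent, the result is 9/11 = 81.8% and the target is still met.

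Nor do the documents show that the bias runs upward. That requires m < a.

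**Conclusion.** The point holds as a mismatch between the target and its calculation. Followed as written, 8.3.2 can report a figure that is not the quantity 8.1 defines. The size is (1-c)(a-m) on a pooled reading. Under an assumed 85% reported adherence, 90% completion leaves the target undecided and 95% completion leaves it met. The verdict is in doubt only if surveys stay missing and reported adherence is near 80%, and the documents supply neither figure.

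The unit of >80% also needs settling, and that part does not depend on missing surveys. Both should be fixed because this is the primary endpoint and the remedy is cheap. The text gives no ground for saying that the result will be wrong or that a decision hangs on it.

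**What to change.** Amend 8.3.2 as follows:

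1. Keep the completed-survey figure and report the survey completion rate beside it.
2. Add a lower bound, with unreported delivered meals counted as not eaten, and an upper bound, with them counted as eaten. Take both over the meals delivered to every enrolled participant up to her last delivery, including women later withdrawn or lost.
3. Take deliveries from delivery confirmations where they exist and from the orders staff submit otherwise. Say that orders only approximate receipt.
4. If the bounds straddle 80%, state that the target is undecided.

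In 8.1, name one unit for >80% (pooled meals, participant mean, or share of participants eating at least 80% of their meals) and compute the main figure and both bounds on it.

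The cost is a short paragraph of wording and a little more analysis, largely from order records that already arise. The reported result may be less favourable or less definite. No new visits or participants are needed, and the bounds can be computed even if data collection has ended.

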8.3.3 ANALYSIS OF THE SECONDARY ENDPOINT(S)

For secondary endpoints, study participation rate (percentage of eligible subjects who agreed to participate out of those who were screened) and retention rate (percentage of enrolled participants

who complete follow-up) will be calculated and reported. Visual representation of the flow of participants through the study will be reported through a CONSORT diagram. Change in participant satisfaction with the diet will be reported as the mean total diet satisfaction score, as well as the mean scores on subscales for Cost Factor and Planning & Preparation Factor, at baseline and follow-up will be reported.¹

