6.2 SUBJECT DISCONTINUATION/WITHDRAWAL FROM THE STUDY

Subjects are free to withdraw from participation in the study at any time upon request.

An investigator may discontinue or withdraw a subject from the study for the following reasons:

- Significant study intervention non-compliance

- If any clinical adverse event (AE), laboratory abnormality, or other medical condition or situation occurs such that continued participation in the study would not be in the best interest of the subject

Subjects who sign the informed consent form, receive the study intervention, and subsequently withdraw, or are withdrawn or discontinued from the study, will not be replaced.

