Intervention Data Collection: All N=11 women who enroll in the study will receive the study meal delivery intervention. At the baseline visit, women who consent to participate in the study will meet with a trained study staff member who will explain the procedures for placing weekly meal orders and show them how to complete weekly online Qualtrics Surveys which will be sent to participants via email. Participants will be given a study scale and instructed to weigh themselves at least once per week and report their weekly weight measurement on the weekly Qualtrics survey. As part of the weekly emailed Qualtrics survey, participants will also be asked to report intervention adherence (e.g., number of study meals they ate versus others versus that they threw away), adverse events (e.g., flatulence, new or worsening gastroesophageal reflux), and satisfaction with the study meals. Staff will complete weekly calls with participants to obtain their meal orders and to complete a brief check-in to see on how they are doing and utilize motivational interviewing techniques to help women who are struggling to comply with the intervention to problem-solve and develop weekly goals. Staff will document the duration and topics discussed during weekly telephone contacts.

Week 8 Follow-up Visit: This visit will take place during the final week for the study meal delivery intervention. Participants will come to the study laboratory and the visit will take approximately 2-2.5 hours. Participants will be asked to complete the following:

Weight measurements: Participant weight will be measured with participants in light clothing and no shoes.

Questionnaires: At the Follow-up Visit, participants will complete the following questionnaires:

- FORM 04: Pittsburgh Sleep Quality Index (PSQI)
- FORM 05: Perceived Stress Scale (PSS-10)
- FORM 06: Diet Satisfaction (DSAT-28)
- FORM 07: Self-Efficacy
- FORM 08: Barriers to Healthy Eating
- FORM 09: Infant Feeding
- FORM 10: Edinburgh Postnatal Depression Scale (EPDS)
- FORM 11: Multidimensional Scale of Perceived Social Support (MSPSS)
- FORM 12: Nutrition Security Survey
- FORM 13: Health & Demographics Update
- FORM 14: Program Satisfaction
- Household Food Security Survey
- International Physical Activity Questionnaire

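### Section 8.3.3 reports the DSAT-28 change as two visit means, without the within-woman change, its n or its spread, so the precision of the Hypothesis 2b estimate is never shown

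*Combined protocol and SAP*

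**What the plan says.** Section 8.1 states Hypothesis 2b as a direction, with no size or threshold: "Participant reported diet satisfaction will show improvements from baseline to follow-up". The schedule in Section 1.2 and the visit lists in Section 7.1 have the same women complete DSAT-28 at baseline and at week 8.

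The analysis text gives one mean per visit. Section 8.3.1: "Average values of outcome measures (e.g., diet satisfaction) will be calculated for baseline and follow-up". Section 8.3.3: "Change in participant satisfaction with the diet will be reported as the mean total diet satisfaction score", together with means for the Cost Factor and Planning & Preparation subscales, at the two visits. The Section 8.3.3 sentence is grammatically broken, but no reading of it adds a paired n or a measure of spread.

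Four other statements bear on the point:

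- Section 8.3.1 rules out inference: "No formal statistical analyses will be conducted as this was a single group feasibility study".
- Section 8.2 warns that "effect estimates based on small pilot studies are too imprecise and should not be used to inform future trials".
- Section 8.3.3 also plans a retention rate and a flow chart: "Visual representation of the flow of participants through the study will be reported through a CONSORT diagram".
- Section 8.3.5 plans unspecified descriptive statistics for the outcome measures, at baseline only.

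On numbers, Section 7.1 says "All N=11 women who enroll in the study will receive the study meal delivery intervention". Under Section 6.2, women who receive the intervention and "subsequently withdraw, or are withdrawn or discontinued from the study, will not be replaced".

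**The concern.** Hypothesis 2b concerns movement within women, and the data are paired. Two visit means give a direction and a size. They do not show whether most women moved the same way or whether a few large changes in both directions happened to net out. Section 2.1 says the findings will guide refinements to the intervention, and a reader using DSAT-28 for that purpose could not tell a consistent rise from noise.

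A second, smaller issue is who is counted. Nothing in Section 8.3.3 requires the two means to cover the same women. If some women are lost and the baseline mean uses everyone enrolled, part of the apparent change reflects who left, in either direction.

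**Working it through.** The documents give no precision or power figure for this endpoint to reproduce; Section 8.2 says no formal power calculation was done.

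**Inputs from the documents.** 11 women (Sections 1.1 and 7.1). Attrition target below 20% (Section 8.1). Losses: 1/11 = 9.1%, 2/11 = 18.2%, 3/11 = 27.3%. The target is therefore met with 9 to 11 completers.

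**Assumptions.** The documents give no DSAT-28 SD and no correlation between visits. Results are in units of the single-visit SD, taken as equal at both visits, with correlation r = 0.3, 0.5 or 0.7.

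**Step 1: spread of the change.** SD of change = sqrt(2(1 − r)), which is 1.183, 1.000 and 0.775 at the three correlations. The same visit means and SDs fit all three values, so visit summaries cannot supply it.

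**Step 2: precision of the mean change.** The 95% half-width with m paired women is t(0.975, m − 1) × sqrt(2(1 − r)/m).

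| m | t | r = 0.3 | r = 0.5 | r = 0.7 |
|---|---|---|---|---|
| 11 | 2.228 | 0.795 | 0.672 | 0.520 |
| 10 | 2.262 | 0.846 | 0.715 | 0.554 |
| 9 | 2.306 | 0.910 | 0.769 | 0.595 |

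**Step 3: one pair of means, different precision.** Take an assumed rise of 0.6 SD in 11 women:

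- r = 0.3: 0.6 ± 0.795, or −0.19 to 1.39
- r = 0.5: 0.6 ± 0.672, or −0.07 to 1.27
- r = 0.7: 0.6 ± 0.520, or 0.08 to 1.12

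The planned output would be identical in all three cases.

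**Step 4: shift from a change in who is counted.** Suppose no woman changes, the baseline mean uses all 11, and the follow-up mean uses completers only. The apparent change is (number lost / 11) × (completer minus non-completer baseline mean). With assumed gaps of 0.5, 1.0 and 1.5 SD:

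- 2 lost: 0.1818 × gap = 0.091, 0.182, 0.273 SD
- 1 lost: 0.0909 × gap = 0.045, 0.091, 0.136 SD

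It looks like improvement if the lost women began with lower scores and like decline if they began with higher ones. With complete data it is zero.

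**Step 5: can the gap be filled from other planned output?** The retention rate and CONSORT diagram count women who complete follow-up. Section 2.3.1 lets participants skip items or stop an assessment, so fewer may have both DSAT-28 scores. A baseline SD under Section 8.3.5 would help little: by Step 1, even SDs at both visits leave the SD of change undetermined.

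**The case against.** The strongest reply is that this is a declared choice. The study is a feasibility pilot aimed at process data. The plan disclaims formal analysis, warns that small-pilot estimates are imprecise, and attaches no threshold to Hypothesis 2b. A reader will know there were about 9 to 11 women and no control group. Refinements can draw on more direct sources: weekly meal-satisfaction reports, the program satisfaction form and the exit interviews (Section 7.1). A 95% interval could itself be read as formal inference, and whether it excludes zero invites a significance reading.

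Much of this stands. The absence of tests is reasonable, the general warning is there, no stated decision turns on DSAT-28, and every magnitude above rests on assumed inputs. It is also fair that the interval is the least essential part of the remedy: n, mean and SD of the change would already meet the concern.

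It does not remove the point. A general warning does not say how imprecise this estimate is. Summarising paired change is description, and an interval without a test or decision rule is compatible with Section 8.3.1. The plan already undertakes to report change; the summary it names cannot show how variable that change was.

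**Conclusion.** The concern holds. For a directional hypothesis on paired data, the plan names a summary that omits the paired n and the spread of change and does not fix the same women for both means. The point estimate is sound with complete data; what is missing is its precision. If 9 to 11 women have both scores, the 95% half-width runs from 0.520 SD (11 women, r = 0.7) to 0.910 SD (9 women, r = 0.3), assuming equal visit SDs. The effect of who is counted is conditional and smaller: 0.05 to 0.27 SD with one or two losses at the assumed gaps, and zero with none.

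The importance is modest, since this is a descriptive secondary measure. The change is still worth making, because the better summary comes from data already collected.

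**What to change.** In Section 8.3.3, define change as follow-up minus baseline in women with both scores. Report its n, mean, SD and a descriptive 95% t interval, for the total score and the two named subscales. Give the n behind each visit mean as well. State that the interval carries no test and no pass/fail rule, in keeping with Section 8.3.1. Add one sentence saying that pairing does not cure selective loss of follow-up scores, regression to the mean or the lack of a control group.

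The cost is a few words in the plan and a few lines of analysis, with no new data. The result will look less certain than two bare means.
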